m-CCRP Care Coordinator: The m-CCRP revolves around the central figure of a care coordinator who will organize and align recovery resources. The care coordinator is a registered nurse whose scope of practice includes health coaching, case managing, community organizing, and nursing care provider. She has received additional education in the following areas: a)

recognizing the symptoms of PICS; monitoring the biopsychosocial needs and outcomes of ICU survivors; c) monitoring negative effects of medications; d) monitoring caregiver burden; e) delivering cognitive, physical, and psychological recovery protocols; f) enhancing the self-management capacity of patients and their informal caregivers; g) communicating and coordinating care with primary and specialty healthcare providers; h) coordinating community resources; and assisting patients and caregivers in developing symptom management skills.

The care coordinator will be responsible for conducting the home and facility visits; collaborating with the m-CCRP interdisciplinary team (see below); maintaining communication with the patient's primary care provider and specialists; conducting root-cause analysis for any preventable hospitalization or emergency department visit; implementing the individualized care plans; and monitoring the effectiveness of these care plans (Box 1).

The care coordinator will be responsible for a new patient panel of 70 patients at any given time-point and will be supervised by the m-CCRP team.

Box 1: m-CCRP Care Coordinator Services

- Self-Management Skills Enhancement
- Support groups
- Continuous access to care coordinator via telephone support
- Medications Reconciliation
- Cognitive Protocol (Paper and computer based cognitive training focused on memory, attention, executive function)³⁴
- Physical protocol (Multimodal exercises focused on seated aerobic and progressive resistance training)³⁵
- Psychological protocol (Problem solving therapy, cognitive behavioral therapy, SSRIs per PCP)³⁶
- Monitoring caregiver's emotional health
- Managing transitional care
- Managing acute care needs
- Root-Cause analysis of re-hospitalization or emergency room visits

m-CCRP interdisciplinary team:

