Research assistants will perform blinded in-person outcomes assessments similar to the baseline assessment using the same instruments (SF-36, RBANS MOCA, Trails A and B, SPPB, 2 minute step test, PTSS-10, employment questions, PHQ-9, GAD-7, and ISI-7) at 3, 6, and 12 . Figure 4 summarizes the study flow. We will employ multiple techniques to ensure concealment of outcomes assessment.^{91,92} Our research assistants will be trained not to inquire about study assignments. They will be conducting structured assessments that do not provide room for qualitative interviewing that should prevent unblinding. They will not be involved in study assignments and treatment administrations. Subjects will be instructed not to discuss their therapy with the research assistants. Loss of information could occur if subjects are unable to complete outcome assessments. To estimate the treatment effect in key domains, a "step-down" battery, consisting of a subset of outcome measures, will be administered when a participant is not able to tolerate the full outcome assessments. This "step-down" battery may also be administered via phone if subject is unable to complete an in-person assessment for the 3, 6 or 12 month outcomes.

Attention Control:

The study research coordinator will identify the primary care providers of patients in the attention control group and ensures appointment at the time of hospital discharge. The patients will receive a guide for ICU survivors containing phone numbers for relevant community resources, education on caregiver coping skills, and legal and financial advice. In addition, the attention control group will receive scripted phone calls by an independent care coordinator assistant not involved in any outcomes assessments. The calls frequency will be similar to the visit frequency of intervention arm (within one week post randomization) within two weeks post first phone call, afterwards twice per month for first six months, and once per month for the next six months). The phone calls will follow a script designed to ask the patients regarding their physical, cognitive, emotional and general wellbeing (see ICU survivors guide). Patients will be directed to the phone guide provided at the time of discharge. For those

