We will use the Repeatable Battery for the Assessment of Neuropsychological Status (RBANS).⁴³ The RBANS was developed for the dual purposes of identifying and characterizing abnormal cognitive decline and a neuropsychological screening battery for adults aged 12-90 years. The entire battery takes 30 minutes to administer, and yields scaled scores for five cognitive domains (Immediate Memory, Visuospatial Construction, Language, Attention, and Delayed Memory). The RBANS has been tested and validated in neurologic, psychiatric, and healthy samples. RBANS has two versions and we will counterbalance for forms across the occasion of measurement to control for minor differences attributable to version.

Physical Performance:

Physical recovery will be assessed via the Short Physical Performance Battery (SPPB), a validated objective assessment.⁴⁴ The SPPB yields a performance score of 0-12 (0-4 poor, 5-7 intermediate, 8-12 good). A difference of 1 point indicates significant change in function.

Depression and Anxiety symptoms:

We will use the Patient Health Questionnaire–9 (PHQ-9)^{45,46} and Generalized Anxiety Disorder Scale (GAD-7)^{47,48} to determine the impact of the intervention on ARF survivors' mood and anxiety. The PHQ-9 is a nine-item depression scale with a total score from 0 to 27 and the GAD-7 is a seven-item anxiety scale with a total score from 0 to 21. Both of these scales are derived from the Patient Health Questionnaire, have good internal consistency, and test-retest reliability as well as convergent, construct, criterion, procedural and factorial validity for the diagnosis of major depression and general anxiety disorder.⁴⁵⁻⁴⁸

Acute Health Care Utilization:

In addition to patient reported emergency department and hospital admission data, we will use the local data-warehouse to capture all of the data needed to determine utilization. Furthermore, we will also use the data from the Indiana Network for Patient Care (INPC) to complement any data use outside of our health system. INPC is the primary health information exchange in the state of Indiana and it provides data for acute care services from all of the health care systems within the state of Indiana. We will determine the number of emergency department visits and the number of re-hospitalizations during follow-up as well as the diagnoses associated with each utilization episode.

Other Data Measures:

Table 7 below shows other data that will be collected.

Data Collection:

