Trained staff using Research Electronic Data Capture (REDCap) will collect all data.

Table 7: Other Data Measures

Variables	Method of Collection
Patient demographics(age, gender, race , education, Body Mass Index)	Electronic Medical Records
Comorbidity-level & Chronic co-morbidities	Charlson comorbidity index score ⁹⁶
Prior history of depression & anxiety	Electronic Medical records
Medications	Electronic Medical records/Patient/caregiver
Severity of illness	APACHE-II ⁹⁷ through medical records at ICU admission
Cognitive status prior to admission	LAR interview using the IQCODE ⁹⁸
Functional status prior to admission	ADL, IADL (Katz, Lawton scales) ^{88,89}
Reason for ICU admission and hospitalization	Electronic Medical records
Duration of mechanical ventilation, noninvasive positive pressure ventilation or high flow nasal canal. delirium, length of ICU and hospital stay	Electronic Medical records, CAM-ICU 7

IQCODE: Informant Questionnaire on Cognitive Decline in Elderly; APACHE: Acute Physiology and Chronic Health Evaluation; ADL: Activities of daily living; IADL: Instrumental activities of daily living. LAR: Legally Authorized representative

9. Privacy/Confidentiality Issues

Loss of confidentiality is a risk in this type of data collection. Our data management and quality assurance techniques have proven effective in past trials in maintaining confidentiality and all study personnel have completed training in Human Subjects Research and HIPAA standards.

10. Follow-up and Record Retention

This is a five year study and study documents will be destroyed seven years after the end date of the study.

11. References:

2. Joint Commission Resources. Improving Care in the ICU, 1st Edition. Oakbrook Terrace, Illinois: *Joint Commission Resources*, 2004.
3. Society of Critical Care Medicine. Critical Care Units: A Descriptive Analysis, 1st Edition. Des Plaines, Illinois: *Society of Critical Care Medicine*, 2005.

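### Could patient-reported ED visits and admissions be counted differently in the two arms under Secondary Aim 2?

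*Combined protocol and SAP*

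**What the plan says.** Secondary Specific Aim 2 compares emergency department (ED) visits and re-hospitalizations between m-CCRP and attention control. Section 8, *Acute Health Care Utilization*, gives the sources: "In addition to patient reported emergency department and hospital admission data, we will use the local data-warehouse to capture all of the data" that the counts require. INPC is added for care outside the health system and is described as a source that "provides data for acute care services from all of the health care systems within the state of Indiana". The section then plans to count ED visits and re-hospitalizations and to record the diagnoses for each episode.

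The only statement on who collects data is general: "Trained staff using Research Electronic Data Capture (REDCap) will collect all data" (Section 8, *Data Collection*). The blinded 3, 6 and 12-month assessments (Section 5) list their instruments, ending with "PTSS-10, employment questions, PHQ-9, GAD-7, and ISI-7". No utilization item is among them.

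Control patients receive "scripted phone calls by an independent care coordinator assistant not involved in any outcomes assessments". On timing, the plan says: "The calls frequency will be similar to the visit frequency of intervention arm". On content: "The phone calls will follow a script designed to ask the patients regarding their physical, cognitive, emotional and general wellbeing".

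In the m-CCRP arm, the care coordinator's duties include "conducting root-cause analysis for any preventable hospitalization or emergency department visit" and a home visit within 72 hours of a hospital discharge.

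**The concern.** An event count can be compared between arms only if events are found equally well in both. Here one of the three sources is patient report, with no stated interviewer, schedule, recall window, common question set or rule for removing duplicates. The control caller stands outside outcome assessment, and the blinded visits list no question on utilization. The only contacts that follow a hospital event belong to the intervention.

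Suppose the coordinator's knowledge fed the counts and records were incomplete. More of the true events would then be found in the m-CCRP arm. The comparison would shift against the intervention, and a real reduction in utilization could be understated. Aim 2 would then partly measure how closely patients were watched rather than how often they used acute care.

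**Working it through.** **What the text supports.** For the bias to arise, three things must hold together: records miss a material share of events; patient report recovers that share unequally by arm; and events known only from patient report are counted.

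- On the first, Section 8 describes INPC as covering every health care system in Indiana, and Section 3 excludes patients living outside greater Indianapolis. Completeness is not quantified, but high capture is the natural reading.
- On the second, Section 5 sets similar contact frequency in the two arms, blinds the outcome assessors, and keeps the coordinator's instruments separate from the outcome instruments. Root-cause analysis and the 72-hour visit are described as parts of the intervention, not as outcome collection.
- On the third, Section 8 lists patient report as a source but never says that an event known only from patient report, or only to the coordinator, enters the count.

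**Size if all three did hold.** The plan has no figure to reproduce. Section 8 states no event rate, effect measure or model for utilization, so the rate ratio used here is itself an assumption. Let *c* be the share of true events found in the records, equal in both arms, and *p* the share of the remaining events recovered by patient report. Then

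detection in an arm = c + (1 − c) × p, and spurious ratio = detection in m-CCRP ÷ detection in control.

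| c | p = 0.80 vs 0.40 | p = 0.80 vs 0.60 | Assumed true ratio 0.85 appears as (0.80 vs 0.40) |
|---|---|---|---|
| 1.00 | 1.000/1.000 = 1.000 | 1.000/1.000 = 1.000 | 0.850 |
| 0.98 | 0.996/0.988 = 1.008 | 0.996/0.992 = 1.004 | 0.857 |
| 0.95 | 0.990/0.970 = 1.021 | 0.990/0.980 = 1.010 | 0.868 |
| 0.80 | 0.960/0.880 = 1.091 | 0.960/0.920 = 1.043 | 0.927 |

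If *p* is the same in both arms, the ratio is exactly 1 whatever *c* is.

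**Against sampling error.** The target of 620 randomized 1:1 gives 310 per arm. At an assumed one event per patient-year, Poisson and with no dropout, the standard error of the log rate ratio is √(1/310 + 1/310) = 0.080. Then ln(1.008)/0.080 ≈ 0.10 and ln(1.021)/0.080 ≈ 0.26: a tenth and a quarter of a standard error. At 80% capture, ln(1.091)/0.080 ≈ 1.1.

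**Effect on the test.** Take a wider contrast of 90% against 50% recovery, equal true rates, 0.5 or 1.5 events per patient-year, and Poisson or overdispersed counts (dispersion 1). A two-sided 5% Wald test then rejects in about 5–6% of trials at 95% capture, 9–24% at 80%, and 36–91% at 50%. The excess rejections point against m-CCRP, so this mechanism does not produce false claims of benefit.

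**Opposite direction.** If false or duplicate reports equal to 5% of true events stayed in the control counts only, the ratio at c = 1.00 would be 1/1.05 = 0.952. No passage describes coordinators correcting reports in their arm, so this has no footing in the text.

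**Records only, as an alternative.** With 80% against 40% recovery and a true ratio of 0.85, dropping patient report multiplies the standard error by √{[1/(0.85c) + 1/c] ÷ [1/(0.85 × detection in m-CCRP) + 1/detection in control]}. This gives 1.000, 1.006, 1.016 and 1.073 at c = 1.00, 0.98, 0.95 and 0.80.

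**The case for a change.** The strongest case for a change is that the asymmetry is concrete and the remedy is cheap. The coordinator's visits are logged in the EMR-ABC software, which Section 5 says can pass data to analysis datasets, so a route exists and no rule closes it. Matched contact frequency does not mean matched questions about hospital events. The blinded assessments are said to be structured, so an unlisted utilization question cannot simply be presumed. If records are nearly complete, patient report adds little while leaving an arm-dependent path open. A count from the warehouse and INPC alone, drawn blind to arm, would need only a change of wording and would cost at most 1.6% in standard error at 95% capture or better.

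The omission stands: Section 8 does not give the collector, the timing or the reconciliation rule. The rest is weaker. An export function in care software is not a plan to count its contents. The study-flow figure and the full call script are not in the available text, so a utilization item there cannot be excluded. A records-only count also gives up events outside INPC's reach, and the documents do not establish that such losses would be equal in the two arms. Keeping patient report for completeness or leaving it out for neutrality is a choice on which reasonable statisticians differ. Near-complete records also make the choice matter little either way.

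**Conclusion.** No change to the plan is called for. The gap is real but operational, and following the plan as written is not shown to give a wrong result. Ordinary practice would fill it: ask both arms the same questions through blinded staff, match reports to records, and leave out events known only through the intervention.

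With capture of 95% or more, the possible distortion is a ratio of 1.000 to 1.021, at most about a quarter of a standard error under the stated assumptions. The conclusion depends on records being close to complete, which the documents suggest but do not quantify. At 80% capture the ratio could reach 1.091 (1.089 under the 90% against 50% contrast), and the point would carry weight if unequal reports were also counted. Aim 2 is a secondary aim, and the only direction with any basis in the text works against the intervention.

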Hypothesis: ARF survivors randomized to m-CCRP will have lower health care utilization as measured by emergency department visits and re-hospitalizations, compared to those randomized to attention control.

3. Inclusion/Exclusion Criteria

Inclusion Criteria

- At least 18 years of age
- Hospitalized in the ICU
- Diagnosed with Acute Respiratory Failure (ARF) requiring greater than or equal to 24 hours of mechanical ventilation or noninvasive positive pressure ventilation or high flow nasal canula.
- Discharged to home, skilled nursing facility, sub-acute rehabilitation care, or long-term acute care
- English speaking
- Able to consent either in-person or through legally authorized representative
- Have access to a telephone

Exclusion Criteria

- Hospitalized to a regular non-ICU ward
- Diagnosis of cancer with life expectancy less than 1 year
- Admitted with ischemic or hemorrhagic cerebrovascular accident, traumatic brain injury, or undergoing neurosurgery
- History of dementing illnesses and other neurodegenerative disease such as Alzheimer's disease, Parkinson's disease, or vascular dementia (confirmed by EMR), or current prescription of anti-dementia medication, or ruled out by Functional Activities Questionnaire (FAQ) score defining dementia
- Unable to complete study questionnaire due to severe hearing loss
- Legally blind
- Pregnant (assessed by urine pregnancy test) or nursing
- Living outside the greater Indianapolis area
- Recent history of alcohol abuse > 5 drinks per day or substance abuse consistently over the last 3 months
- Status post tracheostomy and not eligible for a speaking valve
- Incarcerated at the time of study enrollment
- Schizophrenia or bipolar disorder (confirmed by EMR)
- Homelessness
- Illiterate

4. Enrollment/Randomization

Recruitment Targets:

ARF survivors will be recruited from three local tertiary care hospitals: 1) Indiana University Health Methodist, 2) University Hospital, and 3) Eskenazi Health. Recruitment from three hospitals with different demographics will increase the generalizability of our program in addition to achieving the target recruitment of enrolling 620 ARF survivors in our study.

Recruitment Procedures:

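### Aim 2 has no baseline for ED visits and readmissions: collecting prior-year counts, if the records reach back, would cheaply add precision of uncertain size

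*Combined protocol and SAP*

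**What the plan says.** The Aim 2 hypothesis (section 2) is that the m-CCRP arm "will have lower health care utilization as measured by emergency department visits and re-hospitalizations". Section 8, Acute Health Care Utilization, defines the variables: "We will determine the number of emergency department visits and the number of re-hospitalizations during follow-up", together with the diagnosis for each episode. There are three sources: patient report; the local warehouse ("we will use the local data-warehouse to capture all of the data needed to determine utilization"); and the Indiana Network for Patient Care (INPC), of which the protocol says "it provides data for acute care services from all of the health care systems within the state of Indiana". No look-back period is given for either record source.

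Table 7, in section 8, lists the remaining baseline data: demographics, comorbidity ("Charlson comorbidity index score"), history of depression and anxiety, medications, APACHE-II, pre-admission cognition and function, reason for admission, and details of the index stay. It has no row for earlier ED visits or hospitalizations.

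The SF-36, RBANS, SPPB, PHQ-9 and GAD-7 all belong to the Initial Evaluation, which comes before randomization (section 4). Randomization is 1:1, stratified by hospital only. The text states no analysis model and no covariates for Aim 2.

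**The concern.** Aim 2 is the only aim whose outcome has no pre-randomization counterpart. Visit counts are usually skewed, with a few frequent users carrying much of the variance, and a patient's own earlier count is the most direct measure of that tendency. Stratifying by hospital does not balance frequent users, and the baseline comparison planned in section 8 cannot describe a variable that is not collected.

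What is at stake is the width of the confidence interval for the Aim 2 effect. If prior and later use are well correlated, the trial gives up precision that a longer query window could recover without enrolling anyone else.

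**Working it through.** **1. The plan's own figure.** The only sample-size figure is the recruitment target ("achieving the target recruitment of enrolling 620 ARF survivors in our study"), that is 620 / 2 = 310 per arm. It comes without alpha, power, effect, event rate, dispersion or dropout, and is not tied to Aim 2. It cannot be reproduced, so everything below rests on assumed inputs.

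**2. Inputs.** From the documents: N = 620, 1:1 allocation, 12 months of follow-up. Assumed: two-sided alpha 0.05; mean 1.0-1.5 events per year; gamma frailty variance 1-2; rate ratio 0.75; and r, the correlation between prior-year and follow-up counts.

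**3. Linear approximation.** Adjusted variance = (1 - r²) × unadjusted variance. Take an effect that gives 80% power unadjusted, which is (1.960 + 0.842) × √(2/310) = 0.225 SD. Adjusted power is then Φ(2.802/√(1 - r²) - 1.960), and the equivalent unadjusted N is 620/(1 - r²).

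| r | Variance cut | Power | Equivalent N |
|---|---|---|---|
| 0.2 | 4% | 81.6% | 646 |
| 0.3 | 9% | 83.6% | 681 |
| 0.4 | 16% | 86.4% | 738 |
| 0.5 | 25% | 89.9% | 827 |
| 0.6 | 36% | 93.8% | 969 |

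**4. Simulated counts.** These used 620 patients and 400 replicates per setting. Gamma frailties in the two years were correlated, and a Poisson log-link model with robust standard errors was fitted with and without log(1 + prior-year count).

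| Mean, frailty variance | Count correlation | Variance cut for log rate ratio |
|---|---|---|
| 1.0, 1 | 0.13 | 2.8% |
| 1.0, 2 | 0.15 | 2.9% |
| 1.5, 1 | 0.16 | 2.0% |
| 1.5, 2 | 0.17 | 0.5% |
| 1.0, 1 | 0.28 | 3.9% |
| 1.5, 1 | 0.33 | 12.8% |
| 1.0, 2 | 0.34 | 11.0% |
| 1.5, 2 | 0.40 | 15.2% |
| 1.0, 1 | 0.44 | 20.2% |
| 1.5, 1 | 0.52 | 26.5% |
| 1.0, 2 | 0.58 | 31.7% |
| 1.5, 2 | 0.65 | 34.9% |

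The true log rate ratio is ln 0.75 = -0.288. Mean estimates ran from -0.281 to -0.295 without the covariate and from -0.278 to -0.295 with it. Leaving the covariate out therefore did not shift the estimate.

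**5. Simulation error and cross-checks.** At a correlation of 0.19 (mean 1, frailty variance 1), 4,000 replicates gave a variance ratio of 0.957, a cut of about 4%. Batches of 200 replicates from that setting ranged from 0.90 to 1.00 (SD 0.03), so a 9% cut seen near 0.2 in a run of that size is within noise. At 400 replicates the SD is about 0.03/√2 = 0.02. A run of 1,500 replicates gave cuts of about 5% at 0.20, 6% at 0.30, 22% at 0.48 and 39% at 0.66. Negative binomial fits gave model-based ratios of 0.96 at 0.20, 0.89 at 0.35, 0.81 at 0.45 and 0.66 at 0.62, so the pattern does not depend on the choice of count model.

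**6. Combined range.** The cut is about 4-5% at a correlation of 0.2, about 5-15% at 0.3-0.4, and about 20-39% at 0.45-0.66. The equivalent N at the extremes is 620/0.96 = 646 and 620/0.61 = 1,016.

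**The case against.** The strongest reply is that this is an optional refinement of unknown value on a secondary aim. A critical illness separates the two years, and section 2 says more than half of survivors have lasting morbidity, so a low correlation is plausible. In that case the gain is a few percent. The comorbidity index, APACHE-II and functional status are already collected and would absorb part of the gain if they were used. All of this stands, and it is why the size is given as a range. It does not remove the point: one prespecified covariate costs almost nothing in precision among 620 patients, even at low correlation.

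A reader might infer three stronger things that the documents do not support:

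- **That the plan discards a covariate.** No Aim 2 model is visible, so none is shown to be included or excluded. The reference list has works on missing data and survival modeling that the visible text never cites, so analysis text may exist elsewhere, though that is only an inference. What can be shown is that prior use is not listed for collection.
- **That prior-year data exist for every patient.** The two record sources are described for capturing outcomes. Excluding people who live outside greater Indianapolis says nothing about how long the others have lived there. Availability is plausible and needs confirming.
- **That the result would be biased, or that chance imbalance could pass for an effect beyond the stated error rate.** Randomization already allows for chance imbalance. The cost is precision only.

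**Conclusion.** The point holds as a cheap improvement. The plan defines Aim 2 utilization for follow-up only and lists no prior ED or hospital use, so it lacks the most direct baseline covariate for these counts. The size rests wholly on an assumed correlation: slight at 0.2 or below, modest at 0.3-0.4, and material from about 0.45. The figures also assume the event rates and frailty variances above, complete look-back, and no other adjustment. If other Table 7 variables enter the model, the added gain is smaller. The validity of the randomized comparison is not in question.

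**What to change.** 1. Confirm with the holders of the warehouse and INPC data how far back the records go and how complete they are.
2. If look-back is adequate, add two rows to Table 7: number of ED visits and number of hospitalizations in the 12 months before the index admission. Exclude the index stay and its own ED visit. Draw both from the same query for every randomized patient.
3. Before unblinded analysis, prespecify for each Aim 2 count a negative binomial model with arm, hospital and log(1 + prior-year count). Include an offset for log observed follow-up time, with time censored at death or withdrawal. Without the offset, patients who die or leave early would count as low users.
4. Keep the outcome sources that section 8 already plans, patient report included.

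The cost is a longer query window and some added analysis wording, with no added burden on patients. Prior use outside the covered systems will be missed. Because the covariate predates randomization, this is expected equally in both arms and only weakens the gain.
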